BAD	biologically active dose
BSA	body surface area
BUN	blood urea nitrogen
C	cycle
CBC	complete blood count
CL	clearance
CLB _{oralB}	apparent clearance after oral administration
CB _{maxB}	maximum plasma concentration
CMP	comprehensive metabolic panel
CR	complete remission
CRi	complete remission (with incomplete blood counts)
CRp	complete remission (with incomplete platelet recovery)
CRF	case report form
CTCAE	Common Terminology Criteria for Adverse Events
D	Day
DISC	Data Integrity and Safety Committee
dL	deciliter
DLT	dose-limiting toxicity
DNA	deoxyribonucleic acid
ECG	electrocardiogram
ECOG	Eastern Cooperative Oncology Group
EMD	extramedullary disease
FISH	fluorescence in situ hybridization
GCP	Good Clinical Practice
GI	gastrointestinal
HI	hematologic improvement (see Appendix D)
HMA	Hypomethylating agent
ICF	informed consent form

ICH	International Conference on Harmonization
IPSS	International Prognostic Scoring System
IRB	Institutional Review Board
IV	intravenous
IWG	International Working Group
Ke	elimination rate constant
LC-MS/MS	high performance liquid chromatography/tandem mass spectrometry
LDH	lactic dehydrogenase
MCH	mean corpuscular hemoglobin
MCHC	mean corpuscular hemoglobin concentration
MCV	mean corpuscular volume
MDS	myelodysplastic syndromes
mg	milligram
MTD	maximum tolerated dose
NOAEL	no observed adverse effect level
OS	overall survival
PCR	polymerase chain reaction
PFS	progression free survival
PI	principal investigator
PML	promyelocytic leukemia
PR	partial remission
PT	prothrombin time
PTT	partial thromboplastin time
RBC	red blood cells
RNA	ribonucleic acid
SAE	serious adverse event
SC	subcutaneous
SD	stable disease
SGOT	serum glutamic oxaloacetic transaminase (also AST)
SGPT	serum glutamic pyruvate transaminase (also ALT)
$t_{1/2}$	terminal elimination half-life
T_{max}	time to maximum plasma concentration
UF	University of Florida
UFHCC	University of Florida Health Cancer Center
ULN	upper limit of normal
US	United States
WBC	white blood cell
WHO	World Health Organization

PROTOCOL SYNOPSIS

Title:	A Phase Ib/II Clinical Trial of Oral Ciprofloxacin and Etoposide in Subjects with Resistant Acute Myeloid Leukemia (AML)
Rationale:	There is a paucity of treatment options for subjects with resistant AML. Recently AML has been shown to be a multi-genetic disease with sub-clonal architecture that evolves spontaneously and in response to treatment. Chemotherapy-resistant leukemic clones can quickly gain dominance by “survival of the fittest” dynamics. One way of targeting minor yet resistant clones is to augment the effectiveness of current chemotherapy drugs. Hromas et al. discovered the importance of the Metnase complex in repairing chemotherapy related DNA damage in leukemia and other cancers (1-3). Screening studies identified ciprofloxacin as a Metnase inhibitor that chemosensitizes leukemic myeloblasts to etoposide chemotherapy (4). The non-overlapping toxicity profiles of ciprofloxacin and etoposide, and their additive effectiveness in this model, make these agents attractive candidates for use in combination in subjects with resistant AML.
Primary Objective:	
In subjects with resistant AML, to
 
 Phase 1b: Establish the maximum tolerated dose (MTD) of oral ciprofloxacin when given in combination with a fixed dose of oral etoposide to subjects with resistant AML. Phase II: Determine the complete response (CR, CRi, and CRp, see Appendix A) rate to treatment with ciprofloxacin and etoposide at the MTD in adults with resistant AML.
Secondary Objectives:	
In subjects with resistant AML, to
 
 Determine the safety and feasibility of treatment with oral ciprofloxacin and etoposide; Measure duration of complete response, of progression free survival and of overall survival following treatment with oral ciprofloxacin and etoposide; and Estimate the incidence of Grade ≥ 3 adverse events following treatment with ciprofloxacin and etoposide.
Study Design:	This is an open-label, single arm, Phase Ib/II study of oral ciprofloxacin and etoposide in subjects with resistant AML. This study is designed to evaluate the complete response rate, the safety profile, and biologic activity of the combination of oral ciprofloxacin and etoposide in subjects with resistant AML. For both study phases, all subjects will receive 1 cycle of induction. At the end of Cycle 1, subjects who demonstrate progressive disease will have completed study treatment. For any subject who demonstrates stable disease or a

partial response, a second cycle of induction will be given. No subject will receive more than 2 cycles of induction.

Phase Ib:

In the **Phase Ib** portion of the study, subjects will be enrolled in cohorts of three (3) in a traditional 3+3 study design (5). The starting dose is level “0” and includes: ciprofloxacin 750 mg orally twice daily on Days 1 - 10 and etoposide 200 mg orally once daily on Days 2 – 8. During the first cycle of treatment, subjects will be individually assessed for safety and dose limiting toxicity (DLT) for the purpose of determining the MTD of ciprofloxacin. The MTD will be defined as the highest dose of ciprofloxacin at which < 33% of the subjects treated at a given dose level experience a DLT (See [Figure 1](#)). The **Phase Ib** portion of this study ends when a MTD is identified among the three planned dose levels (See [Table 2](#)).

Subjects withdrawn before Cycle 1 Day 1 (C1D1) will not be evaluable for dose escalation decisions and will be replaced in their treatment cohort. A subject is evaluable for dose-escalation decisions provided: they receive all drug doses and remain on study until evaluation at Cycle 1 Day 28 without a DLT; or they experience a DLT during Cycle 1. Subjects who miss any etoposide or ciprofloxacin doses or withdraw from study without a DLT and prior to Cycle 1 Day 28 are not evaluable for dose escalation decisions and will be replaced in their cohort of treatment.

During dose escalation no more than 3 subjects will be treated simultaneously at any given dose level. The **Phase Ib** portion of this study will not be complete until > 28 days after accrual of the last subject.

Phase II:

Enrollment in the **Phase II** portion of the study will begin once the MTD has been determined. After Cycle 1, subjects with progressive disease will be removed from the study. Other study participants will continue to receive a second 28-day cycle of ciprofloxacin and etoposide at the MTD or until one of the following occurs: disease progression, unacceptable toxicity, consent withdrawal, completion of Cycle 2, or termination of the study.

Dose Limiting Toxicity (DLT)

DLT will be defined as any of the following events that are considered to be related to treatment with ciprofloxacin and etoposide. For the purpose of dose-escalation and MTD determination, only DLTs that occur during the first cycle of oral ciprofloxacin and etoposide will be considered. These include:

1. Any Grade \geq 3 non-hematologic toxicity, except alopecia; and vomiting or nausea uncontrolled by medical management;

	
 2. Any treatment-related effect that results in a subject missing more than 25% of ciprofloxacin or etoposide doses; 3. Any non-hematologic toxicity considered to be related to ciprofloxacin or etoposide that results in a delay of Cycle 2 by > 14 days; 4. Grade 4 neutropenia (absolute neutrophil count < 500/mm³) in subjects with baseline ANC levels > 500/mm³ persisting up to Day 42 after the start treatment, in the absence of leukemia; 5. Grade 3 or greater QTc prolongation developing after the start of therapy with oral ciprofloxacin; and/or 6. Any episode of tendon rupture. 
Prior to commencement of Phase II, DLT's and records of toxicity will be reviewed by the Data Integrity and Safety Committee (DISC).

Inclusion/ Exclusion Criteria:
	
Inclusion criteria - All of the following must apply:
 
 A. Age ≥ 18 years. B. Diagnosis of AML confirmed by review of bone marrow pathology at the University of Florida. C. Patients with relapsed and or refractory AML 
 • who failed to achieve CR or CRi after at least one cycle of induction chemotherapy and not suitable for second cycle of standard intensive chemotherapy, • who have progressed after 1 cycle of HMA or intolerant to HMA therapy and not suitable for standard induction chemotherapy regimens. • who have relapsed after any duration of response, D. Per the treating physician, the subject must have a life expectancy of ≥ 4 weeks. E. Subject performance status must be ECOG 0, 1, or 2 (See Appendix B). F. Subject must have a total bilirubin ≤ 2 mg/dL and AST and ALT ≤ 2.5 times upper limit of normal. G. Subject must have serum creatinine < 2 mg/dL. H. Females of child-bearing potential (i.e., women who are premenopausal or not surgically sterile) may participate, provided they meet the following conditions: 
 ○ Must agree to use physician-approved contraceptive methods throughout the study and for 6 months following the last dose of ciprofloxacin and/or etoposide. Adequate forms of contraception are abstinence, double barrier methods (e.g., condoms with spermicidal jelly or foam and diaphragm with spermicidal jelly or foam), oral, depot, or injectable contraceptives, intrauterine devices, and tubal ligation. ○ Must have a negative serum pregnancy test within 7 days prior to beginning treatment on this study.

	
I. Males with female partners of child-bearing potential must agree to use physician-approved contraceptive methods (e.g., abstinence, condoms, vasectomy) throughout the study and should avoid conceiving children for 6 months following the last dose of ciprofloxacin and/or etoposide.
 
J. Subjects must have provided written informed consent, and demonstrated the willingness and ability to comply with all study-related procedures.
 
Exclusion criteria - None of the following can apply:
 
A. History of allergic or significant adverse reaction (e.g., anaphylaxis, prolonged QTc, or severe tendonitis) to ciprofloxacin or etoposide.
 
B. Acute promyelocytic leukemia (APL) with t(15;17).
 
C. Prolonged baseline QTc, defined as QTc interval > 470 msec in women and > 450 msec in men, or > 480 msec for subjects with a bundle branch block.
 
D. Uncontrolled clinically significant infection. Subjects with fever (temperature $\geq 38.3^{\circ}\text{C}$) thought to be related to leukemia are eligible assuming that blood cultures are negative during the 7 days prior to Cycle 1 Day 1 and there is no clinical evidence of active infection (e.g., negative or stable radiographs and negative physical examination).
 
E. Ongoing, symptomatic Clostridium difficile infection. Subjects who are asymptomatic with negative stool for C. difficile may participate.
 
F. Pregnant and/or nursing.
 
G. History of Myasthenia Gravis.
 
H. Treatment with any anticancer therapy (standard or investigational) within 14 days prior to the first dose of ciprofloxacin or less than full recovery (\leq CTCAE Grade 1) from the clinically significant toxic effects of that treatment. The use of hydroxyurea is allowed only during the first 14 days of cycle 1.

Study Duration and Dates:
	
 • It is estimated that the subject recruitment period will be approximately 48 months. No subject will receive more than 2 cycles of therapy from Day 1 of Cycle 1. • Data regarding disease status and overall survival will be collected monthly until disease progression, death or until 3 years from the on-study date.

Safety Assessments:	
Subjects will be evaluated weekly during and for at least 28 days following the last cycle of chemotherapy. Assessments will include (See Table 1):
 
 • Interval history, review of systems, medications, new allergies, and physical examination with vital sign measurements; • Weekly laboratory assessments, including a CBC with differential and CMP; and • Toxicity assessment per the NIH Common Toxicity Criteria Adverse Event (CTCAE) version 4.
Efficacy Assessments:	
Efficacy parameters used to assess response include hemoglobin, ANC, platelet count, circulating blasts, and bone marrow aspirate and/or biopsy.

Sample Size Estimation	
In prior clinical trials of oral etoposide in resistant AML the CR rate has been approximately 20%. It is expect that the combination of etoposide with ciprofloxacin will improve CR to 40%. In order to detect this difference with type I error rate of 0.10 and power of 80%, when the true response rate is 40%, a minimum of 24 evaluable subjects will be treated in Phase II based on the Simon’s two-stage MiniMax design. Accounting for 15-20% drop out rate, a total of 30 subjects will need to be recruited to this phase.

Table 1. Study Events Schedule

Assessment	Screen (≤ 21 days prior to Day 1)	Cycle 1					Cycle 2		End of Treat- ment ¹² ± 7days	Long- Term Follow Up ¹³
		Day 1	Day 8±2	Day 15±2	Day 22±2	Day 28±2	Days 1, 8, 15, 22±2	Day 28±2		
Signed Informed Consent	X									
Demographics	X									
Medical /Treatment History	X									
Medication History ¹	X	X	X	X	X	X	X	X	X	
Interval History/Physical Examination	X	X	X	X	X	X	X	X	X	
Toxicity Assessment		X	X	X	X	X	X	X	X	
Review of Systems		X	X	X	X	X	X	X	X	
Weight	X	X	X	X	X	X	X	X	X	
ECOG Performance Status	X	X	X	X	X	X	X	X	X	
12-lead electrocardiogram (ECG) ²	X		X			X			X	
Vital Signs ³	X	X	X	X	X	X	X	X	X	
Hematology Laboratory Evaluations ⁴	X	X	X	X	X	X	X	X	X	
Blood Chemistry Laboratory Evaluations ⁵	X	X	X	X	X	X	X	X	X	
Serum Pregnancy Test (females) ⁶	X					X		X	X	
Administer Ciprofloxacin ⁷		X	X				X			
Administer Etoposide ⁸			X				X			
Bone Marrow Aspirate and/or Biopsy ⁹	X					X		X	X	
Adverse Events Assessments ¹¹	X	X	X	X	X	X ¹³	X	X	X	
Survival Assessment										X

¹ Document all medications taken during the two (2) weeks prior to screening and throughout and for 28 days after last treatment.

² Includes: rhythm, rate, and PR, QRS, and QTc intervals.

³ Includes: systolic and diastolic blood pressure, pulse rate, respiratory rate, and temperature.

⁴ Complete CBC including: hemoglobin, hematocrit, platelet and white blood cell count (WBC) with differential including circulating blasts and absolute neutrophil count.

⁵ BUN, creatinine, uric acid, total bilirubin, AST, ALT, alkaline phosphatase, LDH, sodium, potassium, calcium, magnesium, phosphorous, bicarbonate, chloride, glucose, albumin, and total protein.

⁶ Serum pregnancy test within 1 week of Cycle 1 Day 1 for females of childbearing potential. Repeat within one week prior to first day of each subsequent cycle.

⁷ Ciprofloxacin will be administered orally twice daily on Days 1 to 10 of a 28-day cycle.

⁸ Etoposide 200 mg will be administered orally once daily on Days 2 to 8 of a 28-day cycle.

⁹ The screening bone marrow assessment must be performed within 42 days of Cycle 1 Day 1 and must be reviewed at UF. If bone marrow analysis results from outside lab is used to confirm diagnosis, slides must be made available to be read by UF pathologist. This must confirm a diagnosis of AML, non-M3. In case of archived marrow used for eligibility or bone marrow inaspirable or slides unavailable to be read by UF pathologist, and there is greater than 10% blast present, peripheral blood may be collected for flow cytometry.

¹¹ Monitoring for SAEs and AEs starts the day patient signs the informed consent form (ICF), continuing throughout the study. Subjects who have received at least one dose of study drug and discontinue prematurely (regardless of reason) will be followed for any adverse events that occur during the study until 28 days (± 2 days) following the last dose of study treatment (i.e., the Follow-up Visit).

¹² End of treatment visit will occur at CID28 visit in subjects with progressive disease or at study withdrawal if the date does not correspond to a protocol-specified visit. Additional follow-up will include an assessment for the evaluation of AEs and concomitant medications 28 days (± 7 days) after the last dose of study medication. Other assessments will be performed as necessary by the treating physician.

¹³ All subjects will be followed monthly until: disease progression, death, or until 3 years from the on-study date.

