3.3 Phase Ib

3.3.1 Dose Escalation and De-Escalation

The dose escalation phase of the study will utilize a standard “3+3” design to establish the MTD of oral ciprofloxacin in combination with a fixed dose of etoposide (200 mg daily on days 2-8). Ciprofloxacin will be given on days 1-10 at one of three dose levels shown in [Table 2](#). The MTD will be defined as the level associated with a < 1/3 chance of DLT. To summarize: (See [Figure 1](#))

- 1) Three subjects are initially treated at dose Level 0 (ciprofloxacin 750 mg twice daily).
 - a) If none of these experience DLT, then dose will be escalated to Level +1.
 - b) If one of these experiences DLT, then up to three more subjects are treated at Dose Level 1. If one or more of these develops DLT, then the MTD is considered to be exceeded and dose will be reduced to Level -1. If none of these additional subjects develop a DLT then the dose will be escalated to Level +1.
 - c) If 2/3 of these subjects experience DLT, then the MTD is considered to be exceeded and dose is reduced to Dose Level -1.
- 2) If the dose is escalated to Dose Level +1, the same process will be followed to determine if this is the MTD (no further escalation).
- 3) If the dose is reduced to Level -1, then the same process will be followed to determine if this is the MTD. If Dose Level -1 is above the MTD the study will be closed and it will be concluded that treatment with this combination at effective doses is not safe.

Table 2. Planned Dose Levels

Dose Level	Drug	Dose	Frequency	Schedule
0	Ciprofloxacin Etoposide	750mg 200mg	Twice Daily Once Daily	D1-10 D2-8
+1	Ciprofloxacin Etoposide	1000mg 200mg	Twice Daily Once Daily	D1-10 D2-8
-1	Ciprofloxacin Etoposide	500mg 200mg	Twice Daily Once Daily	D1-10 D2-8

[figure not shown]
Subjects withdrawn before Cycle 1 Day 1 (C1D1) will not be evaluable for dose escalation decisions and will be replaced in their treatment cohort. A subject is evaluable for dose-escalation decisions provided: they receive all drug doses and remain on study until evaluation at Cycle 1 Day 28 without a DLT; or they experience a DLT during Cycle 1. Subjects who miss any etoposide or ciprofloxacin doses or withdraw from study without a DLT and prior to Cycle 1, day 28 are not evaluable for dose escalation decisions and will be replaced in their cohort of treatment.

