3. SELECTION OF SUBJECTS

3.1 Number of Subjects

The number of subjects enrolled in Phase Ib to be 8-24 depending upon toxicity, after accounting for a 25% drop-out rate during the first 28-day cycle. In Phase II, up to 44 subjects with relapsed and/or refractory AML will be enrolled. Justification for sample size in phase II is provided in [Section 11.1](#). Subjects in this study can be of any race, gender and ethnic group.

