14.4 Appendix D: Statistical Characteristics of the “3+3” Design

Probabilities of Stopping or Continuing Dose Escalation for Given Probabilities of DLT Associated with the Dose Level

True Probability of DLT at a Dose Level	0.05	0.1	0.2	0.33	0.4	0.5	0.6	0.67	0.7	0.8
Probability of Dose Escalation Based on 3 or 6 Subjects (2 or more DLTs)	0.97	0.91	0.71	0.43	0.31	0.17	0.08	0.04	0.03	0.01
Probability of Ceasing Dose Escalation Based on 3 or 6 Subjects (2 or more DLTs)	0.03	0.09	0.29	0.57	0.69	0.83	0.92	0.96	0.97	0.99
Probability Based on only 3 Subjects (0 DLT)	0.86	0.73	0.51	0.30	0.22	0.13	0.06	0.04	0.03	0.01

Key: DLT = dose limiting toxicity

The probability that dose escalation will cease is at least 92% when the DLT probability is > 60%. If the true probability of DLT for a dose level is at least 33%, the probability of stopping dose escalation is at least 57%. If the true probability of DLT for a dose level is less than 10%, the probability of stopping dose escalation is less than 10%. The probability of dose escalation continuing is at least 91% when the DLT probability is < 10%.

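### As the text is written, the dose carried into Phase II can be declared the MTD on 0 DLTs in three subjects, which gives weak support for a DLT probability below 1/3; a pass at the top level also does not show that an MTD was reached.

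*Combined protocol and SAP*

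**What the plan says.** The synopsis (Study Design, Phase Ib) takes the MTD to be the "highest dose of ciprofloxacin at which < 33% of the subjects treated at a given dose level experience a DLT" and says that Phase Ib "ends when a MTD is identified among the three planned dose levels". Section 3.3.1 words it differently: "The MTD will be defined as the level associated with a < 1/3 chance of DLT".

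The steps in Section 3.3.1 start with three subjects at Level 0. "If none of these experience DLT, then dose will be escalated to Level +1". Three more subjects are treated only if exactly one of the first three has a DLT, and the level then passes if none of the added three has one. For Level +1, "the same process will be followed to determine if this is the MTD (no further escalation". Level -1 is handled in the same way.

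Section 3.4 opens Phase II once the MTD is determined. Section 3.3.2 has the Data Integrity and Safety Committee (DISC) review DLTs and toxicity first, without tying that review to a number of subjects. On size, the Number of Subjects section says "The number of subjects enrolled in Phase Ib to be 8-24 depending upon toxicity", allowing for 25% drop-out. Appendix D tabulates the chance of 0 DLTs in three and the chance of passing a level on three or six subjects.

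Figure 1, cited both by the synopsis definition and by the steps in 3.3.1, was not available in the text reviewed.

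**The concern.** In the lower part of a 3+3 ladder, passing on 0/3 is only permission to look higher. At Level +1 there is nothing higher, so the same 0/3 becomes the final evidence for the declared dose. The gap is not confined to the top. If Level 0 passes on 0/3 and Level +1 then fails, the synopsis definition makes Level 0 the MTD on three subjects, and no step returns to it. Level -1 can also be accepted on 0/3.

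The MTD is the Phase Ib primary result and fixes the dose for every Phase II subject. Section 3.3.2 counts only DLTs in Cycle 1 of Phase Ib toward the MTD, so DLTs seen later cannot revise it.

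There is also a question of what may be concluded. If Level +1 passes, no level has been shown to exceed tolerance. The data then show that the highest planned dose was tolerated; they do not locate a maximum.

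**Working it through.** **Inputs.** The pass rule is from Section 3.3.1. True DLT probabilities p are taken from the columns of Appendix D. Drop-out of 25% is from Number of Subjects and Section 11.1. The added three subjects are taken as treated at the same level as the first three, as the Appendix D figures require.

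**1. The plan's own figures.** P(0/3) = (1-p)^3. P(pass) = (1-p)^3 + 3p(1-p)^2 × (1-p)^3. At p = 0.33: 0.67^3 = 0.301, and 0.301 + 3 × 0.33 × 0.67^2 × 0.301 = 0.434. Appendix D prints 0.30 and 0.43. All ten columns of both rows reproduce to rounding.

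**2. Written rule against a six-subject rule.** The comparator is at most 1 DLT in six: (1-p)^6 + 6p(1-p)^5.

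| True p | P(0/3) | P(pass), as written | Share of passes on 0/3 | P(at most 1/6) |
|---|---|---|---|---|
| 0.10 | 0.729 | 0.906 | 80% | 0.886 |
| 0.20 | 0.512 | 0.709 | 72% | 0.655 |
| 0.33 | 0.301 | 0.434 | 69% | 0.358 |
| 0.40 | 0.216 | 0.309 | 70% | 0.233 |
| 0.50 | 0.125 | 0.172 | 73% | 0.109 |

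At 0.33 to 0.50, six subjects lower acceptance by 6 to 8 points. At 0.10 and 0.20 they cost 2 and 5 points.

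**3. What the counts support.** One-sided 95% exact upper limits for the DLT probability:
- 0/3: 1 - 0.05^(1/3) = 63%.
- 0/6: 1 - 0.05^(1/6) = 39%.
- 1/6: the p solving (1-p)^6 + 6p(1-p)^5 = 0.05, which is 58%.

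None lies below 1/3.

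**4. How often it arises.** If p = 0.10 at both Level 0 and Level +1 (an assumption), Level +1 is declared the MTD with probability 0.906 × 0.906 = 0.82, and on three subjects with probability 0.906 × 0.729 = 0.66. If Level 0 has p between 0.05 and 0.20 and Level +1 has p = 0.33, Level +1 is declared on 0/3 with probability 0.29 to 0.21; with p = 0.50 at Level +1, 0.12 to 0.09.

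**5. Size.** 6/0.75 = 8 and 18/0.75 = 24 reproduce the stated 8-24. With six required at the chosen level, a path through Levels 0 and +1 uses 3 + 6 = 9 to 6 + 6 = 12 evaluable subjects, or 9/0.75 = 12 to 12/0.75 = 16 enrolled.

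**The case against.** **Figure 1.** It may contain an expansion step that the text omits. The stated ceiling hints at one: the written steps visit at most two levels, so at most 12 evaluable or 16 enrolled, yet 24 are allowed. That may equally be simple budgeting of six at each of three levels. The minimum of 8 fits three subjects at each of two levels, but whether those are Levels 0 and +1 or 0 and -1 cannot be told. This limits the point to the written rule. If the figure has the step, the text should state it.

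**The design was chosen with its properties in view.** Appendix D prints the 0/3 and pass probabilities, and the synopsis confines the search to three planned levels. A reader might infer that the rule breaks the plan's own definition. It does not break the synopsis definition, which is an observed share that 0/3 meets. The weakness is against the Section 3.3.1 definition only.

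**Six subjects do not prove it either.** A reader might infer that six would establish a DLT probability below 1/3. The limits of 39% and 58% show otherwise. The gain is a moderate reduction in risk.

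**There are safeguards.** The DISC reviews toxicity before Phase II and semi-annually, and Section 9.3 has a stage I safety stop at 5 of 14. It would be wrong to say that nothing follows. But none sets a minimum number at the declared dose, and the Section 9.3 rule counts adverse events without grade or relatedness.

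**A Phase II run-in.** A reader might expect the first three Phase II subjects to complete the six at no cost. That still opens Phase II on three subjects. At 25% drop-out all three are evaluable with probability 0.75^3 = 0.42. After 0/3, two or more DLTs in the next three occur with probability 0.10, 0.25 or 0.35 at p = 0.20, 0.33 or 0.40, and those subjects would then not count toward the 14 and 24 at the MTD.

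**Conclusion.** The point holds for the written rule. A level can be carried into Phase II on 0/3, and at true DLT probabilities of 0.33 to 0.50 about 70% of acceptances would rest on three subjects. Requiring six with at most 1 DLT moves acceptance from 0.43, 0.31 and 0.17 to 0.36, 0.23 and 0.11. This is a worthwhile improvement at low cost, not a demonstration that the design is unsafe or that six subjects would settle the matter.

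Calling a passed Level +1 the MTD follows from a definition limited to three planned levels, but it claims a limit that was not observed. Correcting that is a matter of reporting and changes no dose.

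The figures assume independent subjects with a common DLT probability at each level, and a text-only reading.

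**What to change.** 1. In the synopsis and Section 3.3.1, state that the dose carried into Phase II needs six DLT-evaluable subjects with at most 1 DLT, completed within Phase Ib before Phase II opens, whichever level is chosen.
2. Reconcile the synopsis and Section 3.3.1 definitions and Figure 1 with that rule. Step 1b of Section 3.3.1 assigns the added subjects to Dose Level 1 although it describes the Level 0 cohort; this must be reconciled with Table 2.
3. If Level +1 passes, report it as the highest planned dose tolerated and the Phase II dose, with the MTD not reached within the planned levels.

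**Cost.** Up to three more evaluable subjects at the chosen level and about one further 28-day cohort; more if the level is then rejected and the one below also has only three. Filling all three levels to six would need 18/0.75 = 24 enrolled, which is the stated ceiling. The chance of accepting a level with a true DLT probability of 0.10 to 0.20 falls by 2 to 5 points.
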